Assuming that the true response rate for the primary endpoint is actually zero (or as low as 0.1%) in the population of interest of the historical control, the primary efficacy endpoint hypothesis is whether AVXS-101 treated patients achieve a response rate greater than 0.1%.

Based upon preliminary results from the completed Phase 1 clinical trial AVXS-101-CL-101, at least 50% of treated patients in the defined ITT population are expected to achieve the primary efficacy endpoint of sitting without support for at least 10 seconds at any post-procedure visit up to and including 18 months of age. With this assumption for the true response rate of AVXS-101 being in the range of 20%–50%, a sample size of 25 patients would provide power of greater than 95% to detect a significant difference from 0.1% with $\alpha = 0.025$ using a 1-sided exact test for a binomial proportion.

The secondary efficacy endpoint of survival at 14 months of age will be comparing the results observed in the ITT population with the results from the age and gender-matched control patients selected from existing natural history data sets (PNCr). It is anticipated that 75% of patients in the PNCr population would not survive beyond 13.6 months of age, and that these control patients will represent a 25% survival rate based upon the natural history of the disease. Preliminary results from the completed Phase I clinical study, AVXS-101-CL-101, suggest that at least 80% of patients in the ITT population are expected to survive, as defined, through 14 months of age. These assumptions suggest that a sample size of at least 25 patients would provide at least 95% power to detect a significant difference from the historical control with $\alpha = 0.05$ using a 2-sided Fisher's Exact test.

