Based upon preliminary results from the same ongoing Phase 1 clinical trial AVXS-101, at least 80% of treated symptomatic patients with two copies of *SMN2* and without the genetic modifier (c.859G>C) are expected to achieve the secondary efficacy endpoint of survival at or beyond 14 months of age (based upon the definition of survival outlined above). It is anticipated that 75% of patients in the PNCR population would not survive beyond 13.6 months of age, and that these control patients will represent a 25% survival rate based upon the natural history of the disease. Given this efficacy, a sample size of 25 patients would provide power of >90% to detect a significant difference with $\alpha = 0.05$ using a 2-sided Fisher's Exact test, as comparing to those control patients from existing natural history data sets (PNCR, NeuroNext [26]).

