3.11.2. Secondary Efficacy Hypothesis

The secondary efficacy hypothesis to be tested is:

$$H_0: p_{AVXS-101} = p_{PNCR}$$

versus the alternative

$$\mathbf{H}_a: p_{AVXS-101} \neq p_{PNCR}$$

where p is the proportion 14 months of age event-free surviving.

Testing for the primary efficacy endpoint, independent sitting will first be performed using 1-sided exact binomial test. Only if the null hypothesis of equality in proportion of functional independent sitting is rejected at $p < 0.025$, will the secondary efficacy endpoint survival improvement be tested using a 2-sided Fisher's exact test on the ITT population, comparing to patients from the natural observational study (PNCR) at 0.05 significance level. This hierarchy approach strongly prevents the Type I error rate from inflation.

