5.6. PNCR Control Population

The PNCR Natural History dataset is drawn from a large natural history study ([Finkel, 2014](#)) performed on a large cohort of 337 patients with any form of spinal muscular atrophy followed at 3 large, internationally recognized tertiary medical centers with significant expertise in the management of SMA (Harvard University/Boston Children's Hospital, Columbia University and the University of Pennsylvania/Children's Hospital of Philadelphia). Previously identified patients followed in PNCR site clinics and newly diagnosed patients were enrolled. All eligible patients were offered participation in the PNCR study. Study visits were scheduled at baseline and at 2, 4, 6, 9, and 12 months and every 6 months thereafter. The SMA standard of care

guidelines ([Wang, 2007](#)) were used as a basis for providing uniform care among the study sites. For purposes of this study, sitting (for SMA Type 2) was defined as being able to sit independently for >10 seconds; children who were unable at any point to achieve this milestone were classified as SMA Type 1.

A natural history control population is drawn from the PNCr Natural History Dataset ([Finkel, 2014](#)) consisting of all patients with age of onset ≤ 6 months, bi-allelic deletion of *SMN1* (exon 7/8 common homozygous deletion) and 2 copies of *SMN2* for whom enrollment data (retrospective and prospective) is available to determine survival based on the defined criteria. The *SMN2* modifier mutation (c.859G>C) described by Prior and colleagues (Prior, Thomas W., et. al. "A positive modifier of spinal muscular atrophy in the *SMN2* gene." *The American Journal of Human Genetics* 85.3 (2009): 408-413.) was not assessed in the PNCr study cohort. Based on these criteria, 23 patients from the PNCr dataset are included in the control population. Among them, 16 patients reached the combined endpoint of death or the need for a minimum of 16 hours/day of noninvasive ventilation support for a minimum of 14 continuous days by 14 month of age and one patient discontinued the study at age of month 4. The survival rate at 14 months of age is approximately 25% (6/23), of which the control cohort will be used as comparator with ITT population for survival analysis.

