For a participant who develops an acute reversible illness and/or requires perioperative ventilator support, a recovery period not to exceed 21 days following the date of definitive intervention will be instituted. Following this recovery period, the condition will be considered sub-acute and the participant will become evaluable with regards to the surrogate survival endpoint (Requirement of ventilator support of ≥ 16 hours/day for greater than 14 days).

Example: Using this approach it would mean that on day 1, patient A receives definitive intervention for an acute reversible illness resulting in ventilator support for ≥ 16 hours/day. Days 1-21 will be provided to permit recovery from the acute reversible illness. On Day 22, the participant is no longer considered to have an acute illness. Should the participant continue to require ≥ 16 hours/day of ventilator support from day 22 to day 36, he or she shall be considered to meet the surrogate endpoint.

Statistical approach: The proportion surviving event-free to 14 months of age will be computed in the ITT population. Patients who terminate the study prior to reaching 14 months of age for any reason will be considered treatment failures (event).

As a comparator, in a natural history study of SMA Type 1 patients, [Finkel et al \(2014\)](#), 16 patients reached the combined endpoint of death or the need for a minimum of 16 hours/day of noninvasive ventilation support for a minimum of 14 continuous days by 14 month of age, one patient discontinued the study at age of month 4 and 6 patients event-free survived at age of 14 months.

The observed proportion surviving in the current study will be compared to the natural history data (5) of the matching cohort, using a 2-sided Fisher's Exact test, along with the corresponding 95% confidence intervals.

The number of patients survived in each subgroups specified in [Section 6.7](#) will be provided.

Time to death or permanent ventilation through 14 months of age is an additional sensitivity analysis. In case there is at least 1 patient who is event-free, but discontinue study prior to 14-months of age, a sensitivity analysis, based on the approach for time to event, will be carried out. In this analysis, time to event will be censored at 14 months of age or at the date of

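### The PNCR comparator of 6/23 counts one control lost at month 4 as a non-survivor; this slightly favours AVXS-101, and no sensitivity Fisher test addresses it

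*SAP*

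**What the plan says.** The secondary endpoint is survival to 14 months of age without permanent ventilation. SAP 3.11.2 tests it, once the primary endpoint is significant, by a "2-sided Fisher's exact test on the ITT population, comparing to patients from the natural observational study (PNCR) at 0.05 significance level".

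SAP 5.6 describes 23 controls and gives the comparator: "The survival rate at 14 months of age is approximately 25% (6/23), of which the control cohort will be used as comparator". SAP 8.2.1 repeats the breakdown. Besides 16 controls who reached the combined endpoint, "one patient discontinued the study at age of month 4 and 6 patients event-free survived at age of 14 months".

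For the trial's own patients, SAP 6.3 and 8.2.1 set a failure rule: "Patients who terminate the study prior to reaching 14 months of age for any reason will be considered treatment failures (event").

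SAP 8.2.1 also names time to death or permanent ventilation as an additional sensitivity analysis. It is to be carried out "In case there is at least 1 patient who is event-free, but discontinue study prior to 14-months of age". Follow-up is censored at 14 months of age or at discontinuation, and the treated and PNCR curves are compared by log-rank test. The trigger names no cohort.

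**The concern.** The control lost at month 4 is not among the 16 events and not among the 6 survivors, yet stays in the denominator of 23. In the proportion that enters the Fisher test the child therefore counts as a non-survivor.

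Counting a dropout as a failure works in opposite directions in the two cohorts. Among treated infants it lowers the observed AVXS-101 rate and is conservative. Among controls it lowers the rate to be beaten and is anti-conservative. The SAP does not comment on this, and it plans no Fisher comparison at any other control count.

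There is also a tension within SAP 5.6, which restricts the control cohort to patients with enough data to determine survival. Nothing in the documents shows that this child's 14-month status could be determined, so the child's place in the denominator needs a sentence of explanation.

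At stake are the estimated treatment difference, which shifts at any result, and the significance verdict over a narrow band of results. With a fixed external cohort of only 23, one child is worth up to 4.3 percentage points.

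**Working it through.** **Inputs.** Controls: 23, of whom 16 had events, 6 were event-free and 1 was lost at month 4 (SAP 5.6, 8.2.1); 16 + 6 + 1 = 23. Treated: at least 25 ITT infants, 30 planned for enrolment (Protocol 14.2, SAP 3.7). Test: two-sided Fisher, alpha 0.05 (SAP 3.11.2). Assumed survival: control 25% (SAP 3.7); treated, "at least 80% of patients in the ITT population are expected to survive, as defined, through 14 months of age" (Protocol synopsis).

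**The plan's own figures.** SAP 3.7 states that "a sample size of 25 patients would provide power of >90% to detect a significant difference"; the Protocol synopsis states that "a sample size of at least 25 patients would provide at least 95% power to detect a significant difference from the historical control". Exact power, summing binomial probabilities over all tables with Fisher p < 0.05 in favour of AVXS-101 at 80% versus 25%, is 97.6% for 25 versus 23 and 97.9% for 25 versus 25. Both statements hold.

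**Control rate under each handling of the lost child.**

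- Non-survivor (as planned): 6/23 = 26.1%
- Excluded: 6/22 = 27.3%, which is 1.2 points higher
- Event-free: 7/23 = 30.4%, which is 4.3 points higher
- Censored at month 4 (Kaplan-Meier): if e controls had the event before month 4, S(14) = (1 − e/23) × 6/(22 − e). The documents do not give e. At e = 0 this is 6/22 = 27.3%; at the extreme e = 16 it is (7/23) × (6/6) = 30.4%. Censoring therefore gives a rate between those of the two alternatives.

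**Smallest number of treated survivors with Fisher p < 0.05.**

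| Control | N = 25 | p (one fewer) | N = 30 | p (one fewer) |
|---|---|---|---|---|
| 6/23 | 14 | 0.045 (0.083) | 17 | 0.049 (0.055) |
| 6/22 | 15 | 0.039 (0.076) | 17 | 0.049 (0.089) |
| 7/23 | 15 | 0.049 (0.089) | 19 | 0.027 (0.052) |

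At N = 25 the verdict differs only at 14/25 (56%). At N = 30 it differs at 17/30 and 18/30, and only against 7/23.

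**At the planned result, 20/25 = 80%.** Fisher p is 0.0004 against 6/23, 0.0004 against 6/22 and 0.0011 against 7/23. The estimated difference is 80 − 26.1 = 53.9 points, 80 − 27.3 = 52.7 points or 80 − 30.4 = 49.6 points.

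**Chance that the handling matters if true treated survival is 80%.** With the control table fixed and N = 25, P(X ≥ 14) = 0.9985 and P(X ≥ 15) = 0.9944, so P(X = 14) is about 0.4%. With N = 30, P(X ≥ 17) = 0.9991 and P(X ≥ 19) = 0.9905, a gap of about 0.9%.

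**Power if the true control rate were higher.** For 25 versus 23 at 80% treated survival, exact power is 96.2% at a control rate of 27.3% and 93.4% at 30.4%. The second figure is below the synopsis's 95% but above the 90% in SAP 3.7.

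**The case against.** The strongest reply has four parts.

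*The rule is the same in both cohorts.* Early termination counts as failure for treated infants too. Symmetric handling is a recognised choice, and scoring a treated dropout as failed while scoring a control dropout as event-free is a worst case. This stands as a reason not to make 7/23 the main comparator. It does not make the effect neutral, because the same rule biases the comparison in opposite directions in the two cohorts.

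*Event-free survival is the less likely outcome for this child.* Of the 22 controls with known status, 16 (73%) had the event. This also stands: 6/22 is the more neutral figure and 7/23 a bound.

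*The SAP already discloses and partly covers the point.* Both sections list the lost child separately from the 16 events. A reader might infer that the child was recorded as dead or ventilated; the documents do not say so, and the non-survivor status arises only from the arithmetic of 6/23. A reader might also infer that the censored analysis excludes controls. The text does not support that either: the time-to-event analysis is first introduced without a condition, the trigger that follows names no cohort, and the log-rank test covers both. What remains is ambiguity. If only a treated dropout triggers the analysis and none occurs, it may not be run.

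*The impact is very small.* A reader might infer that the secondary claim hangs on this child. At the planned survival rate it does not.

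**Conclusion.** The point holds as a small, one-directional weakness in the comparator. Using 6/23 lowers the control rate by 1.2 points relative to exclusion and by 4.3 points relative to the worst case. It lowers the bar by one survivor at N = 25. At N = 30 it lowers the bar by none against 6/22 and by two against 7/23. The significance verdict could change only for treated survival of roughly 56% to 60%, well below the planned 80%, where every version is significant. The stated power is not in error.

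This rests on two assumptions. The lost control's 14-month status is taken as unknown, since neither document gives it or the reason for leaving. The number of control events before month 4 is also not given, so the Kaplan-Meier rate is shown as a range, 27.3% to 30.4%.

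**What to change.** - Keep 6/23 for the main Fisher test.
- In SAP 5.6, state the cohort as 6 event-free, 16 with the event and 1 of unknown status at 14 months. Say why that child meets the cohort's requirement for data sufficient to determine survival.
- In SAP 8.2.1, pre-specify sensitivity Fisher tests at 6/22 and 7/23, and report whether the conclusion holds at each.
- Run the Kaplan-Meier/log-rank comparison unconditionally, with this control censored at month 4.

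The cost is a few lines of SAP text and two extra tests. To claim robustness at 7/23, the sponsor needs one more treated survivor at N = 25 (15 rather than 14) or two more at N = 30 (19 rather than 17). Neither is demanding if treated survival is near 80%.

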5.7. Pharmacokinetic Set

Not applicable for this SAP.

5.8. Pharmacodynamics Set

Not applicable for this SAP.

5.9. Protocol Deviations

All deviations will be recorded in the [REDACTED] database and will be categorized in accordance with ICH E3 Guidelines. As this is a single dose study, protocol deviations will be described; however, there will be no separate statistical analysis.

6. GENERAL ASPECTS FOR STATISTICAL ANALYSIS

6.1. General Methods

All hypothesis testing will be conducted at one-sided with significance level $\alpha=0.025$ or two-sided, at significance level $\alpha=0.05$, as appropriate. Categorical measures, such as percent surviving event-free, will be summarized using count and percentages.

Continuous data, such as CHOP-INTEND scores, will be summarized using count, mean, median, standard deviation (SD), minimum, and maximum. For continuous data specified to be analyzed using parametric procedures, non-parametric procedures will be used if assumptions of parametric tests are not met.

Summary tables, listings, and figures, and statistical analyses will be done using SAS version 9.3 or higher. The primary and secondary efficacy analyses will be conducted on the ITT population. Safety analyses will be conducted on the Safety population.

6.2. Key Definitions

6.2.1. Definition of Baseline

The baseline value refers to the last non-missing measurement collected before gene therapy infusion of study drug. On Study Day 1, all assessments should be performed prior to administering the gene therapy infusion of study drug per protocol. The baseline value is therefore determined by the last non-missing measurement collected on or before the first day of study drug administration. If multiple measurements are recorded on the same day, the last measurement recorded prior to the gene therapy infusion will be used as the baseline value. If these multiple measurements occur at the same time or time is not available, then the average of these measurements (for continuous data) or the worst among these measurements (for categorical data) will be considered as the baseline value. This same baseline value will be used for the treatment and post-treatment periods.

The baseline values will be the first non-missing values collected for the control patients from the PNCR dataset.

6.2.2. Definition of Study Days (Days Relative to the Gene Therapy Infusion)

Study Days are calculated for each time point in the treatment period relative to the gene therapy infusion of study drug. Study Days are negative values when the time point of interest is prior to the study drug infusion day. Study Days are positive values when the time point of interest is after the first study drug dose day. Study Day 1 is the day of the infusion of the gene therapy study drug.

6.2.3. Definition of Final Treatment Value

The first non-missing value on or after the participant reaches 14 months of age will be considered for the purposes of the secondary endpoint survival without permanent ventilation. There is no upper bound for the “14 months” age visit; that is, no visit is too late to represent the “14 months of age” analysis. The earliest visit on or after 420 days of age will be used in the “14 months of age” analysis.

Due to the COVID-19 pandemic, patients with the end of study (EOS) visit planned between Feb, 2020 and Sept, 2020 may not be able to complete the EOS visit in the protocol defined visit window. Based on current guidance, these patients will be allowed to complete the EOS when hospitals reopen for normal operation.

For developmental milestones, CHOP-INTEND score and Bayley scale, the final treatment value for each patient is defined as the first non-missing value on or after the participant reaches 18 months of age (540 days) with an upper limit of 570 days. Thus, the earliest visit between 540 and 570 days of age, inclusive, will be used in the “18 months of age” analysis. For other non-safety measures, the definition of final treatment value will be footnoted in the corresponding tables, listings or figures.

For safety data collected through the EOS visit will be used for safety analysis, no upper bound for final treatment value.

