4.1.2. Secondary Efficacy Endpoints

The secondary efficacy endpoint is survival, defined as avoidance of either (a) death or (b) permanent ventilation through the 14 month of age visit. Permanent ventilation is defined by tracheostomy or requirement of ≥ 16 hours of respiratory assistance per day (via non-invasive ventilatory support) for ≥ 14 consecutive days in the absence of an acute reversible illness, excluding perioperative ventilation. Permanent ventilation, so defined, is considered a surrogate for death.

The respiratory assistance includes but is not limited to BiPAP machines, for example, Philips Trilogy 100 machine. Particularly, Trilogy 100 usage data will be saved in the SD card when patient uses the machine. Data in the SD card will be sent to AveXis by site during clinical visit. Daily usage information will be available when using DirectView software to extract the “compliance summary” from the raw data (.EDF files).

In addition, each site will be asked to verify whether permanent ventilation criteria were met for each patient. If a patient is reported to necessitate permanent ventilation, the date at which permanent ventilation was met will be reported by site.

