6.2.4.2. Supportive (Secondary and exploratory) Efficacy Variables

The secondary efficacy endpoint, event-free survival, is defined as avoidance of any one of the following events up to 14 months of age, whichever occurred first:

- Death, *or*
- Tracheostomy, *or*
- Noninvasive Ventilatory support ≥ 16 -hour per day *and* continuously ≥ 14 days

Usage data for patients using non-invasive ventilatory support will be extracted directly from the device (e.g., Trilogy 100, Trilogy 200, ResMed Stellar) on an SD card, or USB stick and transferred as an external dataset, if available. Average daily use of non-invasive ventilatory support at baseline and monthly be summarized from data recorded on an SD card or USB stick and submitted in a format that is evaluable. If a patient did not have a device with the capability to record usage data at baseline and was using non-invasive ventilatory support prior to screening, the daily usage will be documented in the source documentation. As a secondary analysis, the amount of ventilation support will be categorized into None, $>0-\leq 12$ hours, $>12-\leq 16$ hours, ≥ 16 or permanent ventilation. At each of the above time points, the count and percent of patients in each ventilation support category will be presented.

Supportive (exploratory) efficacy variables are as follows:

- CHOP-INTEND summary score: This is assessed by evaluating the Baseline CHOP-INTEND scores compared to each scheduled visit time points (see [Table 4](#)), collected from patient's CRF. A summary score is obtained by summing the individual best-side scores.
- Achievement of Selected Threshold Scores on CHOP-INTEND: clinically relevant threshold scores were determined for categorizing CHOP-INTEND summary scores: ≥ 40 , ≥ 50 , ≥ 58 .
- Bayley Scales of Infant and Toddler Development[®] version 3: Two domains of motor and adaptive behavior will be assessed from patient's CRF at scheduled visits (see [Table 1](#)) with both raw and scaled scores provided.
- Age at which independent sitting (for 10 seconds) is first achieved.
- Ability to remain independent of ventilator support, defined as requiring no daily ventilator support/usage at 18 months of age.
- Ability to thrive as defined by maintaining the ability to swallow and to maintain weight ($>$ third percentile based on WHO CGRS without need of gastrostomy or other mechanical or non-oral nutritional support at 18 months of age)

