6.4.1. Study Day Based Visit Windows

For efficacy analysis, the time windows specified in [Table 4](#) describe how efficacy data will be assigned to protocol-specified time points, as displayed in the Schedule of Assessments in [SAP Section 3.5.1](#). All time points and corresponding time windows are defined based on Dosing Date.

If more than one efficacy observation for a specific assessment is included in a time window, the assessment closer to the nominal time will be used. If there are two efficacy observations equally distant to the nominal time, the latest one will be used in analyses. Any efficacy assessments occurring outside the analysis windows will be considered an assessment of an unscheduled visit.

Table 4: Study Day Based Visit Window

| Scheduled Visit | Nominal Days (Study Day) | Acceptable Analysis Window in Study Days (Min Day – Max Day) |
|--|--------------------------|--|
| Baseline | - | <1 |
| Month 1 | 30 | 1 to 44 |
| Month 2 | 60 | 45 to 74 |
| Month 3 | 90 | 75 to 104 |
| Month 4 | 120 | 105 to 134 |
| Month 5 | 150 | 135 to 164 |
| Month 6 | 180 | 165 to 194 |
| Month 7 | 210 | 195 to 224 |
| Month 8 | 240 | 225 to 254 |
| Month 9 | 270 | 255 to 284 |
| Month 10 | 300 | 285 to 314 |
| Month 11 | 330 | 315 to 344 |
| Month 12 | 360 | 345 to 374 |
| Month 13 | 390 | 375 to 404 |
| Month 14 | 420 | 405 to 434 |
| Month 15 | 450 | 435 to 464 |
| Month 16 | 480 | 465 to 494 |
| Month 17 | 510 | 495 to 539 |
| Month 18 | 540 | 540 to 569 |
| Month K | K*30 | K*30 to (K+1)*30-1 |
| Final Treatment Visit and 14 Months of Age Analysis Window | | 0 to ≤14 days after patient reaches 14 months of age (420-434 days of age) visit window; 0 to ≤14 days after patient reaches 18 months of age (540 days of age) visit window |

*Depending on age at time of dosing, patients will complete varying number of visits. The patient must complete a visit within 2 weeks after reaching 14 months of age; subsequent visits will be scheduled from that visit date. The patient must also complete the final study visit within 2 weeks after reaching 18 months of age.

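### The SAP runs 14-month survival to the first visit on or after day 420 in two sections and to 14 months of age elsewhere, so treated infants can be followed longer than the controls

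*SAP*

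**What the plan says.** Two SAP sections tie the endpoint to a visit.

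- SAP 6.2.3, naming survival without permanent ventilation: "The first non-missing value on or after the participant reaches 14 months of age will be considered for the purposes of the secondary endpoint". It puts no upper bound on that visit ("that is, no visit is too late to represent the" 14-month assessment) and adds that "The earliest visit on or after 420 days of age will be used in the" analysis.
- SAP 4.1.2 defines survival as "avoidance of either (a) death or (b) permanent ventilation through the 14 month of age visit".

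Three sections tie it to age.

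- SAP 6.2.4.2: event-free survival "is defined as avoidance of any one of the following events up to 14 months of age, whichever occurred first".
- SAP 8.2.1: the proportion event-free to 14 months, time to event censored at 14 months of age or at discontinuation, and each component summarised by 14 months.
- SAP 5.6: PNCR controls are counted as having reached the ventilation endpoint "for a minimum of 14 continuous days by 14 month of age".

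Table 4 in SAP 6.4.1 adds a bounded window, "0 to ≤14 days after patient reaches 14 months of age (420-434 days of age) visit window". The text of that section treats efficacy assessments outside the analysis windows as unscheduled. SAP 4.1.2 and 6.3 have the date of death or permanent ventilation reported for treated patients. No section says which rule prevails.

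**The concern.** Death and permanent ventilation are dated events. Taking the first non-missing value at or after a time point suits a repeated measurement such as CHOP INTEND. It does not suit an endpoint that is complete once the date of the first event is known. Applied to survival, it replaces a fixed age with a cut-off that varies from child to child.

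This is the only hypothesis besides the primary in the testing hierarchy (SAP 8.4), and it is tested against an external control. Follow-up length should be the same in both groups by rule, but here one reading follows treated infants past the age at which controls are cut. The trial is also open-label, so if the choice is left until analysis it will be made with the outcomes in view.

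**Working it through.** **Inputs.** A month is 30 days (SAP 1.2), so 14 months is 14 × 30 = day 420, the figure used in SAP 6.2.3. The 14-month visit is due 0 to 14 days after 14 months is reached (Protocol 7.1, SAP 3.5), so an on-time visit falls on days 420–434. The plan assumes 25 ITT patients, 80% treated survival and 25% control survival, with a 2-sided Fisher's exact test at 0.05 (SAP 3.7). The control cohort has 16 events, 1 early discontinuation and 6 survivors: 16 + 1 + 6 = 23, and 6/23 = 26.1% (SAP 5.6).

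**The plan's own figure.** Exact power is the sum, over all pairs (i, j) with Fisher p ≤ 0.05, of Bin(i; 25, 0.80) × Bin(j; 23, 0.25). This gives 97.6%, or 97.9% with 25 controls. The stated power above 90% is reproduced, so the sample size is not in question.

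**The same child under each rule.**

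| Child | Visit rule (SAP 6.2.3, 4.1.2) | Age rule (SAP 6.2.4.2, 8.2.1) |
|---|---|---|
| Event day 415, visit day 430 | failure | failure |
| Event day 425, visit day 430 (on time) | failure | survivor |
| Event day 450, first visit since day 420 on day 460 | failure, once 6.2.3 takes day 460 as the 14-month visit | survivor |
| Death day 440, no visit since day 420 | no visit value exists under 6.2.3 | survivor |

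The second row needs no missed visit. In that row the main analysis under the visit rule would also disagree with the SAP's own time-to-event sensitivity analysis, which censors at 14 months.

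**Direction.** Moving the treated cut-off later can only add treated events. Controls stay at 14 months. The error therefore lowers the treated rate.

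**Size.** One child is 1/25 = 4 percentage points. Results against 6/23 are:

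| Survivors | Rate | Exact 95% CI | 2-sided Fisher p |
|---|---|---|---|
| 24/25 | 96% | 79.6–99.9% | 4.2 × 10⁻⁷ |
| 23/25 | 92% | 74.0–99.0% | 3.7 × 10⁻⁶ |
| 20/25 | 80% | 59.3–93.2% | 0.00038 |
| 14/25 | 56% | 34.9–75.6% | 0.045 |
| 13/25 | 52% | 31.3–72.2% | 0.083 |

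From the planned 20/25, 20 − 13 = 7 children would have to change status before significance is lost. If one or two expected survivors became failures (80% to 76% or 72%), power would fall from 97.6% to 95.0% or 91.0%.

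**The case against.** The best defence is that SAP 6.2.3 only says which visit represents 14 months and leaves the endpoint to the sections that define it. Event dates are reported, SAP 8.2.1 counts to 14 months, and components and time to event are also anchored there. That may well be the intent. But SAP 6.2.3 names the survival endpoint and speaks of its value, and SAP 4.1.2, which does define the endpoint, separately runs it through the visit. The defence shows how easily the conflict can be resolved. It does not show that the SAP resolves it.

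Three stronger readings are tempting and should not be drawn.

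- **That a child who met the ventilation criterion early and was later weaned would count as a survivor.** Every endpoint section defines survival as avoidance of an event, SAP 6.2.4.2 takes the first event, and permanent ventilation is declared a surrogate for death. Nothing lets later status undo a dated event.
- **That the 420–434 day window in Table 4 makes a child a failure.** A value outside it is only an unscheduled assessment. The survivor/failure split comes from counting to a visit rather than to an age.
- **That exposure commonly runs about four months longer.** Being next seen at 18 months means missing the 14-, 15-, 16- and 17-month visits. Three consecutive visits missed and not rescheduled, other than for hospitalization, are already a listed reason for discontinuation (Protocol 8.3).

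It is also fair to say that the error is conservative, and that nothing in the documents shows any child to be affected.

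**Conclusion.** The point stands as a conflict between stated rules that should be corrected before analysis. It is not a threat to the conclusion on survival. It concerns only treated children with an event dated from day 421 to the first later visit: a span of at most 14 days for an on-time visit, longer if visits are missed. Each such child costs AVXS-101 4 points at n = 25. The reported rate and its interval can move, but a change in the test result would need far more reclassified children than is plausible.

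This rests on the SAP's 30-day month, 25 ITT patients and the control count of 6/23. The 24/25 and 23/25 results are illustrations, not predictions.

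**What to change.** 1. In SAP 6.2.3 and 4.1.2, state that status is decided by the recorded date of death, tracheostomy or first meeting the permanent-ventilation criterion. The patient is a failure if that date is on or before the day 14 months of age (day 420) is reached. A first event stands whatever the later status.
2. Give the cut as a day number. SAP 1.2 rounds age to one decimal, so day 421 (421/30 = 14.03) would otherwise also read as 14.0 months.
3. State that the first contact on or after day 420, however late, only confirms that no earlier event was missed. Amend Table 4 so that its 420–434 day window does not limit that confirmation.
4. Check that SAP 6.2.4.2 and 8.2.1 use the same words, and keep the existing rule that patients who leave before 14 months count as failures.
5. Apply the same age cut to PNCR as far as its event dates allow, and report their precision. SAP 5.6 and 8.2.1 give counts only. The planned log-rank comparison implies that control event times exist, but the SAP does not show that they are known to the day.

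For treated patients this is a wording change, since the event dates are already collected. For the controls it needs a check of the existing dataset. No new data collection, visits or change in sample size is involved.
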